5 STATISTICS

5.1 Statistical analysis plan and sample size calculation

An a priori analysis using G*Power software (version 3.1.7; Heinrich Heine University Düsseldorf, Düsseldorf, Germany) for proportions (using a 2-tailed alpha value of 0.05, and power of 0.80) recommended a sample size of 124 (62 per group), based on previous research (7) reporting a total of 32 injuries (17.5% in intervention group compared to 41.4% in control group) during the 9-month season. The injury incidence rate will be calculated as follows: [(number of events during a specified period)/(total athlete-exposures at risk during a specified period)] x 1000. We will calculate incidence rate ratios together with 95% confidence intervals to assess the risk difference

between the intervention and the control group. The exposure time will be calculated as (1) participation hours and (2) athlete-exposure. The participation hours will be calculated for each group as the sum of the number of exposure hours of each player (match exposure time, training exposure time, total exposure time = match + training hours). The athlete-exposure will be calculated for each group as the number of athletes participating in each game or training session (for example, a team of 10 athletes who participated in 5 games and 50 team practices would accumulate 50 athlete games and 500 athlete practices for a total of 550 athlete-exposures). Differences in participation hours and athlete-exposure between the intervention and control groups will be assessed using the independent t test (if data follows normal distribution) or Mann-Whitney U test (if data does not follow normal distribution). Data analyses will be performed using R. Any deviation from the original statistical plan will be described and justified in the final trial report.

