considerations	period)/(total athlete-exposures at risk during a specified period)] x 1000. We will calculate
	incidence rate ratios together with 95% confidence intervals to assess the risk difference
	between the intervention and the control group.
	Inclusion criteria
	1) ≥16 years of age; 2) >2 years' experience in organized basketball training and competition
Inclusion and	immediately prior to participation in the study; 3) officially registered teams. Exclusion criteria
exclusion criteria	1) regular training takes place less than twice per week; 2) teams already apply an injury
	prevention program or a structured warm-up focusing on neuromuscular control.
	No restrictions will be set according to sex.
	An a priori analysis using G*Power software (version 3.1.7; Heinrich Heine University
Sample size	Düsseldorf, Düsseldorf, Germany) for proportions (using a 2-tailed alpha value of 0.05, and
	power of 0.80) recommended a sample size of 124 (62 per group), based on previous research

	reporting a total of 32 injuries (17.5% in intervention group compared to 41.4% in control group)	
	during the 9-month season.	
Intervention	A specifically designed five-phase (20 min) neuromuscular warm-up protocol will be integrated within the regular training routines. At the beginning of the season, each coach will obtain an exercise manual including a detailed description of the setup, all the exercises (including different difficulty levels), and additional background information concerning posture corrections and proprioception. Intervention components are designed to include running (running straight ahead, running high-knees, running glute-kick, hip out, hip in, leg crossovers), plyometrics, balance, strength (walking lunge, double leg jump – double leg landing, single leg jump to double leg jump, double leg jump – highest point catch – double leg landing, single leg jump – highest point catch – single leg landing, double leg jump – two handed pass, wall sit, ball release core rotations, plank, side plank) and agility drills (mirror forwards and backwards, mirror side shuffle), replicating a basketball-specific workload as recommended from the literature.	
Control	Teams from the control group will be instructed to perform their usual warm-up routine.	

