3.3 Study design

A two-arm, cluster-randomised controlled trial (level of evidence 1) will be adopted in this study, and conducted as a single-centre study in Switzerland. To reduce potential confounding, the teams will be matched by sex and playing level. All teams will be randomly allocated to a control

or intervention group in a 1:1 ratio. The researcher who conduct the randomization will not be involved in the intervention, and recruitment will be completed before randomization. Computer-generated cluster randomization will be conducted using Research Randomizer software (https://www.randomizer.org/).

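### The 124 players and 80% power come from a calculation for independent players, although teams are randomised; the claim has no allowance for clustering.

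*Protocol*

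**What the plan says.** Section 3.3 of the protocol describes the design: "A two-arm, cluster-randomised controlled trial (level of evidence 1) will be adopted in this study". It has teams matched by sex and playing level and then allocated 1:1, and the title also calls the trial cluster-randomised. Section 4.3 speaks of participants being assigned, but it admits whole teams once 70% of the roster has accepted, so the team remains the unit.

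Section 5.1 gives the sample size as a G*Power calculation "for proportions (using a 2-tailed alpha value of 0.05, and power of 0.80) recommended a sample size of 124 (62 per group"). The planning proportions, from previous research over a 9-month season, are "17.5% in intervention group compared to 41.4% in control group". The synopsis repeats the result: "power of 0.80) recommended a sample size of 124 (62 per group), based on previous research".

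Neither place gives a number of teams, a planned number of players per team, an ICC, a design effect or an allowance for dropout. The only team size in section 5.1 is a team of 10, used to illustrate how athlete-exposures are counted.

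**The concern.** Players in one team share a coach, the way the warm-up is delivered, a schedule and the person who reports injuries, so their outcomes are likely to be correlated. When teams are randomised, that correlation inflates the variance of the comparison between arms. The amount of information then depends largely on the number of teams per arm, which the protocol does not state. A two-proportion calculation for independent players takes no account of this.

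What is at stake is the power statement. A reader would take 80% as a property of the cluster design, and an inconclusive result could be weighed against it. The target of 124 could also be met with few teams without anyone noticing that the stated power no longer applies. The protocol itself gives the size and power as finished figures, so a separate analysis plan would not make the statement right.

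**Working it through.** **Inputs from the protocol.** Section 5.1: two-sided alpha 0.05, power 0.80, p1 = 0.175 (intervention), p2 = 0.414 (control), 62 per arm. Section 3.3: teams randomised 1:1.

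**Inputs assumed, because the protocol gives none.** Players per team m = 10 to 12; ICC = 0.01 to 0.10.

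**Step 1: reproduce 62 per arm with independent players.**

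- Two-sided Fisher exact test, full enumeration: power 0.787 at 61 per arm, 0.796 at 62, 0.805 at 63.
- Pooled z test: power = Φ{[|p2 − p1|√n − 1.96√(2p̄q̄)] / √(p1q1 + p2q2)}, with p̄ = 0.2945, 2p̄q̄ = 0.4155 and p1q1 + p2q2 = 0.3870. At n = 62 this is Φ[(1.882 − 1.263)/0.622] = Φ(0.994) = 0.840. Power 0.80 needs 56 per arm.
- Other versions: continuity-corrected z needs 64 per arm, unpooled z 54, arcsine 55.

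Only Fisher comes close to 62 at a power that rounds to 0.80. The match is near and not perfect, since 63 is the first size to reach 0.80. No version that was tried needs a clustering term to arrive at about 62.

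**Step 2: apply clustering to the same 62 per arm.** Design effect DE = 1 + (m − 1) × ICC; effective size per arm = 62/DE, rounded to a whole number for Fisher. For example, m = 10 and ICC = 0.05 give DE = 1 + 9 × 0.05 = 1.45, and 62/1.45 = 42.8.

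| m | ICC | DE | Effective n per arm | Fisher power | Pooled z power | Total N = 2 × ⌈62 × DE⌉ |
|---|---|---|---|---|---|---|
| 10 | 0.01 | 1.09 | 56.9 | 0.758 | 0.807 | 136 |
| 10 | 0.02 | 1.18 | 52.5 | 0.715 | 0.775 | 148 |
| 10 | 0.05 | 1.45 | 42.8 | 0.617 | 0.685 | 180 |
| 10 | 0.10 | 1.90 | 32.6 | 0.465 | 0.565 | 236 |
| 12 | 0.01 | 1.11 | 55.9 | 0.749 | 0.800 | 138 |
| 12 | 0.02 | 1.22 | 50.8 | 0.705 | 0.760 | 152 |
| 12 | 0.05 | 1.55 | 40.0 | 0.573 | 0.655 | 194 |
| 12 | 0.10 | 2.10 | 29.5 | 0.431 | 0.523 | 262 |

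The last column inflates the 62 per arm by the design effect. It shows scale only and is not a proposal to enrol more.

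**Step 3: where the pooled z test crosses 80%.** That test needs 56 effective players per arm, so the limit is ICC = (62/56 − 1)/(m − 1): 0.012 for m = 10 and 0.010 for m = 12.

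**Step 4: few teams.** 124/10 = 12.4 and 124/12 = 10.3, so 124 players are about 10 to 12 teams. A t approximation uses standard error √(0.3870 × DE/62) and 2 × (teams per arm − 1) degrees of freedom. Results at ICC 0, 0.01, 0.02, 0.05 and 0.10:

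- m = 10 (6 teams per arm, 10 df): 0.778, 0.743, 0.709, 0.621, 0.509.
- m = 12 (5 teams per arm, 8 df): 0.755, 0.711, 0.671, 0.569, 0.451.

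**The case against.** Several points on the other side are fair.

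- **The test is inferred.** Section 5.1 does not name Fisher, and on these rounded inputs Fisher first reaches 0.80 at 63 per arm, not 62. This stands: the figure is consistent with that test and no more.
- **The loss may be small.** With a pooled z test 124 independent players have 84% power, and about 80% survives an ICC of 0.01. This also stands, so the size of the loss is not known. At ICC 0.05 the pooled z figure is 66% to 69%, and the t approximation is already below 80% at ICC 0.
- **Matching by sex and playing level may remove some between-team variance.** It may, but the calculation takes no credit for it, and with few teams a matched analysis has few degrees of freedom.
- **124 is a recommended size, not a cap.** Section 4.2 invites teams from three divisions. A reader might infer that the trial will have only 10 to 12 teams, or that it is bound to be underpowered; the protocol supports neither. The point concerns what 124 players deliver.
- **The primary endpoint is an incidence rate.** A reader might take the powers above as the real power of the primary comparison. They are not: they correct the protocol's own calculation, which concerns the proportion of players injured.
- **Timing.** Protocol version 02 is dated 28.09.2022, after the last-participant-out date of 30.06.2022 in the synopsis. On those dates, team numbers and an ICC range added now are disclosure, not prior planning. That affects how the correction is worded, not whether it is needed.

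**Conclusion.** The point holds, as an omission that makes the power statement wrong as written. The protocol randomises teams and claims power 0.80 for 124 players from a calculation that treats players as independent. Under the test that best reproduces the figure, power is 0.796 before clustering, so any positive ICC takes it further below 0.80.

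The size rests on an assumed ICC of 0.01 to 0.10 and 10 to 12 players per team: about 76% down to 43% by Fisher, or 81% down to 52% by pooled z. Confidence is high in the omission and in its direction, and low in any single figure within those ranges. The documents do not support the stronger statement that true power is clearly or greatly below 80%, because they give no ICC and a small one would cost only a few points.

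**What to change.** In section 5.1 and in the synopsis:

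- Describe 124 (62 per group) as the size before clustering, name the test used, and withdraw the unqualified 80% power.
- State the number of teams per arm and the expected consenting players per team.
- Give the resulting power over a stated ICC range, using DE = 1 + (m − 1) × ICC and t-based degrees of freedom from the number of teams.
- Say that these powers refer to the proportion of players injured, not to the incidence rate that is the primary endpoint.
- If the text is revised after the season, say that the cluster figures were added afterwards.

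The cost is a few sentences in two places and a less favourable stated power. The correction requires no extra enrolment and changes no study procedure.

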2 BACKGROUND AND RATIONALE

Basketball is a sport that places high demands on the lower extremities, which can lead to an increased risk of injury. The lower limbs (63.7%) are the most affected injury region in basketball players (1). Two basketball-related injuries that traditionally receive the most attention are ankle sprains and knee injury [particularly of the anterior cruciate ligament (ACL)], accounting for 15% and 23% of all basketball injuries in males and females (2). Sports-related injuries are a substantial contributor to the health care costs in Switzerland, estimated at over 931 million Swiss francs per year, of which the highest costs resulted from ACL reconstruction, particularly in team sports (3). Epidemiological data reveal a worrying increase in the incidence of ACL reconstructions in young athletes (4). An ACL injury has serious consequences for the injured athlete, in terms of not only treatment costs and time lost from sport, but also a greatly increased risk of early osteoarthritis. While ankle sprains are relatively less severe than ACL injury in terms of time lost from sport, prevention efforts are important, considering the increased risk of recurrent sprain, concomitant injury to the talus and peroneal musculature, and the development of chronic ankle instability (5, 6) with subsequent osteoarthritis that can follow initial ankle sprains (7).

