3 STUDY OBJECTIVES AND DESIGN

3.1 Hypothesis and primary objective

Hypothesis:

A specifically designed training program can be effective in reducing the incidence rate of injury in basketball players.

Objective:

The aim of this study is to assess the effectiveness of a specifically designed five-phase neuromuscular warm-up protocol (which incorporates basketball-specific drills) in reducing the incidence rate of injuries.

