3.2 Primary and secondary endpoints

Primary endpoint: Incidence rate of lower extremity injuries

Secondary endpoints:

Incidence rate of ...

- ... overall injuries
- ... severe injuries (lay-off time of more than 28 days)
- ... joint-ligament injuries
- ... muscle injuries
- ... ankle injuries
- ... knee injuries
- ... upper extremity injuries

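### The sample size is never tied to the lower-extremity primary endpoint; if its planning rates count all injuries, the stated 80% power is not shown for that endpoint and could be about 50–59%

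*Protocol*

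**What the plan says.** Section 3.2 of the protocol names the primary endpoint as "Incidence rate of lower extremity injuries". Overall injuries head the separate list of secondary endpoints.

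Section 5.1 sizes the trial for two proportions, "using a 2-tailed alpha value of 0.05, and power of 0.80". It "recommended a sample size of 124 (62 per group"), on the strength of earlier work "reporting a total of 32 injuries (17.5% in intervention group compared to 41.4% in control group") over a nine-month season. The synopsis repeats the calculation. Neither place gives a body region for the 32 injuries. Section 5.1 cites reference 7 for these rates. The reference list gives that entry as a paper on post-traumatic osteoarthritis of the ankle, and Section 2 uses the same number for osteoarthritis after ankle sprain.

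Section 2 gives a general figure for basketball players: "The lower limbs (63.7%) are the most affected injury region". The sample size does not use it.

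Section 3.1 states the hypothesis without a body region: "A specifically designed training program can be effective in reducing the incidence rate of injury in basketball players". The objective there is equally general.

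**The concern.** Three statements that should concern one quantity do not visibly do so. The endpoint is lower-extremity injuries, the planning rates are for injuries without qualification, and the hypothesis is about injuries in general. Elsewhere (Sections 2 and 3.2) the protocol names the lower limb or lower extremity when it means that region, so an unqualified count reads as all injuries.

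If that reading is right, the 80% belongs to a secondary endpoint. Lower-extremity injuries are a subset of all injuries. With the same relative effect there are fewer events and less power. A null result on the primary endpoint could then be taken as evidence of no effect when the trial had little chance of detecting the planned one. The general hypothesis in Section 3.1 adds a smaller problem: it does not say which of the two endpoints it is to be judged on.

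**Working it through.** **Inputs.** From Section 5.1: p₁ = 0.175 (intervention), p₂ = 0.414 (control), two-sided α = 0.05, target power 0.80, n = 62 per group. From Section 2: lower-limb share s = 0.637. From Section 3.3: 1:1 allocation. Players are treated as independent throughout, as in the protocol's own calculation.

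**Step 1: reproduce the protocol's figure.** Fisher's exact test, by full enumeration of both binomials, has power 79.6% at 62 per group and 80.5% at 63. This matches the stated 62. The z test with pooled variance under the null needs 56 per group (64 with continuity correction). Its power is

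Φ{ [ |p₂ − p₁| − 1.96·√(2p̄(1−p̄)/n) ] / √( (p₁(1−p₁) + p₂(1−p₂))/n ) }, with p̄ = (p₁ + p₂)/2.

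At n = 62: (0.239 − 0.1605)/0.0790 = 0.994, and Φ(0.994) = 84.0%.

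**Step 2: scale both arms by the lower-limb share, same relative effect.**

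- Intervention: 0.175 × 0.637 = 0.1115. Control: 0.414 × 0.637 = 0.2637. The ratio stays at 0.42.
- z test: (0.1522 − 0.1374)/0.0688 = 0.215, and Φ(0.215) = 58.5%.
- Fisher: 50.3%.
- 80% power would need 112 per group (Fisher, 80.3%) or 103 per group (z test).

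**Step 3: the same, if the percentages are players injured.** A share of injuries scales the rate, not the probability of being injured. Under a Poisson model the scaled proportion is 1 − (1 − p)^0.637.

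- Intervention: 1 − 0.825^0.637 = 0.115. Control: 1 − 0.586^0.637 = 0.289.
- Power at 62 per group: 60% (Fisher), 67% (z test).

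**Step 4: vary the lower-limb share (assumed values, linear scaling, same relative effect).**

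| Share | Fisher | z test |
|---|---|---|
| 50% | 37.5% | 46.7% |
| 63.7% | 50.3% | 58.5% |
| 80% | 64.7% | 71.3% |
| 90% | 72.7% | 78.1% |

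**Step 5: vary how the effect divides between body sites.** The full reduction is 41.4 − 17.5 = 23.9 percentage points. The control rate is held at 26.4%.

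| Part of the 23.9 points in the lower extremity (assumed) | Intervention rate | Fisher | z test |
|---|---|---|---|
| Half | 14.4% | 29.9% | 37.7% |
| 63.7% (same relative effect) | 11.1% | 50.3% | 58.5% |
| 80% | 7.3% | 77.3% | 82.0% |
| All | 2.5% | 97.7% | 97.4% |

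**Step 6: the other reading.** If 17.5% and 41.4% already count lower-extremity injuries, Step 1 applies as it stands and power is about 80%.

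**The case against.** The strongest reply is that nothing in the protocol says the rates are for all injuries. With two arms listed straight after it, the total of 32 may simply mean both arms added together. If the rates already refer to the lower extremity, there is no shortfall. This stands as a limit on the claim. It does not clear the protocol, because the link to the primary endpoint is then unstated and the citation points elsewhere.

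The meaning of the percentages is also uncertain. A search of whole-number splits of 32 injuries that round to 17.5% and 41.4% finds only 20/114 and 12/29, a very lopsided comparison. They may therefore not be those 32 injuries divided by players, and multiplying them by a share of injuries is an approximation. Step 3 shows that another reasonable scaling gives 60–67%.

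An equal relative effect at all sites is an assumption too. The programme consists largely of running, landing and agility drills, and the background is about knee and ankle injuries, so a larger effect on the lower extremity is plausible. Step 5 shows that power of about 77–82% would then be possible. The 97% case, however, needs the whole reduction to fall in the lower extremity and none elsewhere, which the protocol does not claim.

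A reader might infer, without conditions, that the trial is sized on all injuries and has 50–59% power instead of 80%. The documents do not support that. The 63.7% is a general background figure, tied neither to the planning source nor to either arm, and the body region of the planning injuries is not given.

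Finally, a general aim made specific by a named endpoint is ordinary drafting. That is fair, and the wording of Section 3.1 is only a minor alignment point.

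**Conclusion.** The point holds in conditional form. The protocol does not show that its planning rates belong to its primary endpoint, and the more natural reading is that they do not.

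The loss of power rests on three assumptions: the rates count all injuries, 63.7% of injuries are lower-extremity in each arm, and the relative effect is the same as for all injuries. Power at 62 per group is then about 50–59%, or 60–67% if the percentages are players injured and rates are scaled. At a constant relative effect, every share examined in Step 4 leaves power below 80%. If the third assumption is relaxed, the range is wide: about 30–38% if half of the reduction is in the lower extremity, and about 97% if all of it is. Confidence is high that the link to the primary endpoint is missing, and moderate at most for any single power figure. Clustering by team is a separate matter and is not in these numbers.

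**What to change.** - In Section 5.1 and the synopsis, state which injuries the 17.5% and 41.4% count, and whether they are injuries per player or players injured.
- Correct the citation in Section 5.1 so that it points to the study from which the rates were taken.
- If the rates are for all injuries, replace the 80% with power recomputed for lower-extremity injuries at 62 per group. Give the lower-limb share and the assumed effect on the lower extremity, with a range such as the one above. If they are already lower-extremity rates, say so; the 80% can then stand as a calculation for independent players.
- Reword the hypothesis in Section 3.1 so that the primary one concerns lower-extremity injuries, with overall injuries secondary.

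The cost is a few lines of protocol text. If the rates prove to be for all injuries, the stated power will probably be less favourable.

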4.3 Study procedures

The observation period will comprise one basketball season from September/October 2021 to May/June 2022. To ensure recruitment of participants, an information sheet containing exclusion/inclusion criteria will be distributed to all basketball teams in August 2021. After signing informed consent forms, eligible participants will be assigned to a control or intervention group in a 1:1 ratio. Teams who meet an acceptance rate of 70% from the roster list will be included in the study.

Data on medical history, age, height, body mass, training characteristics, injury history, basketball experience, and competition level will be collected at baseline. Injury characteristics, including location, type, mechanism, as well as time loss from sport will be reported by the coach or other contact person (therapist, medical doctor) on a weekly injury report form to the researcher (blinded to group allocation) via email (23). For each team, the contact person (preferably, but not necessarily the coach) will be instructed to report injuries that occurred during a scheduled match or training session, causing the player to be unable to complete the current match or training session and/or to fully take part in the next match or training session. If an injury requires medical treatment, basketball player will be instructed to obtain the exact diagnosis from the treating physician. Injury rates will be reported as number of injuries per 1000 athlete exposures. Exposure is defined as one athlete participating in one practice or match. Coaches will register individual playing time (min) and absences (due to an injury) for each training session and match during the season.

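### Teams are randomised, but the planned incidence rate ratio is built from group totals with no team or matching term, so its 95% CI is too narrow if team rates still vary after matching

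*Protocol*

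**What the plan says.** Section 3.3 fixes the design: "A two-arm, cluster-randomised controlled trial (level of evidence 1) will be adopted in this study". Before allocation, "the teams will be matched by sex and playing level", and then "All teams will be randomly allocated to a control" or intervention group, 1:1. The tool is named too: "Computer-generated cluster randomization will be conducted using Research Randomizer software".

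Section 5.1, whose title includes the statistical analysis plan, defines the injury rate as events divided by total athlete-exposures, times 1000. It sets the level at which exposure is added up: "The athlete-exposure will be calculated for each group as the number of athletes participating in each game or training session". The comparison follows: "We will calculate incidence rate ratios together with 95% confidence intervals to assess the risk difference".

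The same section sizes the trial at 124 players (62 per group) from two independent proportions, 17.5% and 41.4%, "using a 2-tailed alpha value of 0.05, and power of 0.80". Exposure is compared between groups by an independent t test or a Mann-Whitney test. No team effect, robust variance, team-level summary, ICC, design effect or matching factor appears in the analysis text. Section 4.3 adds wording that reads as individual assignment: "eligible participants will be assigned to a control or intervention group in a 1:1 ratio".

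**The concern.** The analysis text does not follow the randomisation. One event total and one exposure total per arm carry no information on how teams within the arm differ. A confidence interval computed from them can take its variance only from the counts, as if injuries were independent.

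Teammates share a coach, a schedule and usually one person who reports injuries, and the programme reaches players through the coach. Team rates may therefore differ by more than Poisson chance. With few teams per arm, a handful of high-injury or low-injury teams could push the interval away from 1 with no true effect. The primary endpoint, the incidence rate of lower extremity injuries, would then be reported with too much certainty.

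**Working it through.** **1. The plan's own figure.** Inputs from section 5.1: 17.5% v 41.4%, two-sided alpha 0.05, power 0.80. Exact power of Fisher's test for independent proportions is 0.796 at 62 per group and 0.805 at 63. The usual normal formulas give 56 per group (pooled, no continuity correction) or 64 (with correction). So 62 per group is, to rounding, a Fisher calculation on independent players. No allowance was made for clustering: the design effect is 1.

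**2. Design effect in ICC terms.** Assumed: m = 10 players per team (the size in section 5.1's exposure example) and ICC 0.01 to 0.10. Design effect DE = 1 + (m − 1) × ICC. The true standard error of the log ratio is √DE times the naive one. Actual type I error of the naive analysis = 2 × [1 − Φ(1.96/√DE)].

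| ICC | DE | SE multiplier | Type I error |
|---|---|---|---|
| 0.01 | 1.09 | 1.04 | 6.0% |
| 0.02 | 1.18 | 1.09 | 7.1% |
| 0.05 | 1.45 | 1.20 | 10.4% |
| 0.10 | 1.90 | 1.38 | 15.5% |

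On the log scale the interval should thus be 4% to 38% wider. With m = 15 the error runs from 6.6% to 20.6%.

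**3. Effect on an interval at the planning figures.** Assume equal exposure and treat injured players as event counts: 62 × 0.175 ≈ 10.9 and 62 × 0.414 ≈ 25.7, ratio 0.42. Naive SE of the log ratio = √(1/10.9 + 1/25.7) ≈ 0.36, giving a 95% CI of about 0.21 to 0.86. With DE 1.45 it is about 0.18 to 0.99, and with DE 1.90 about 0.16 to 1.12.

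**4. Simulation on the rate scale, with and without a gain from matching.** Assumed: 62/10 ≈ 6 teams of 10 per arm and no true effect. The lower-extremity rate is 0.414 × 0.637 = 0.264 per player-season, where 63.7% is the lower-limb share in section 2. That product assumes that 41.4% counts all injuries. Test: pooled log ratio with SE √(1/E₁ + 1/E₂), where E₁ and E₂ are the event totals, at nominal 5%.

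| Between-team CV | No gain from matching | Half of team variance shared within pairs | 80% shared |
|---|---|---|---|
| 0 | 4.6% | – | – |
| 0.2 | 5-6% | about 5% | about 5% |
| 0.4 | 9% | 7% | 5.5% |
| 0.5 | 12% | 8% | 6% |
| 0.6 | 15% | 10% | 7% |

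An analytic cross-check of the first column uses DE = 1 + 10 × 0.264 × CV². At CV 0.4 this is 1.42, and the formula in step 2 gives 10%, close to the simulated 9%. A higher event rate raises the error: at 0.414 per player-season with no gain from matching, CV 0.5 gives about 16%.

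**5. Team-level alternatives in the same setting.** With no shared variance, an unmatched t test on team rates stays near 5%. With half the variance shared within pairs it falls to about 3.0-3.7% at CV 0.4-0.6, which wastes power. A matched comparison of team rates stays near 5%.

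**The case against.** The protocol names no method for the confidence interval and never says that clustering will be ignored. A Poisson mixed model or GEE also yields an incidence rate ratio with a 95% CI, and a separate statistical analysis plan, not seen here, could specify one. That stands in part. A reader might infer that the interval is certainly too narrow and that the false-positive rate certainly exceeds 5%. The documents do not support this: it depends on team variation beyond Poisson that remains after matching, and no figure for that is given. Nor does the protocol state how repeat injuries in one player enter the variance, so nothing is counted for them here. What remains is that section 5.1 does give a method: group totals, a ratio of group rates, and a sample size that reproduces as individual-level. It does not defer to another document, and it requires any departure from the original statistical plan to be justified.

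Matching is the second objection. It removes part of the team variance from the comparison between arms, and the table shows a marked gain. This also stands, so figures without matching are the unfavourable end. At low team variation the excess over 5% is about a percentage point or less.

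Third, 10 players is only an example, 124 is a recommended size rather than a cap, and three divisions are invited, so the number of teams could be larger. More teams would not remove the excess: with 10 teams of 12 per arm, a rate of 0.414 and no gain from matching, CV 0.3 gives about 10%.

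Finally, section 4.3's wording might suggest that players are randomised individually, which would make the analysis fit. The title and the explicit statements in section 3.3 make the team the randomised unit. Section 4.3 should be reconciled with them.

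**Conclusion.** The concern holds in conditional form. The primary comparison in section 5.1 does not reflect the team as the randomised unit or the matching in section 3.3. The direction of the error is settled for any team variation beyond Poisson that survives matching. Its size cannot be fixed from the protocol. Under the stated assumptions the type I error lies between about 5% (little team variation, or most of it matched away) and about 15% (CV 0.6 or ICC 0.10, no gain from matching). At the planning effect, ICC 0.05 brings the upper limit from 0.86 to 0.99, and ICC 0.10 takes it past 1, so the primary conclusion could change.

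**What to change.** In section 5.1, replace the group-total ratio for the primary endpoint by an analysis that respects both team and matching. Suitable choices are:

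- a Poisson or negative binomial model of lower-extremity injury counts with log(athlete-exposures) as offset, sex and playing level as covariates, and either a team random effect or team-clustered GEE, with a small-sample correction;
- a matched comparison of team rates;
- a permutation test that permutes teams within the matching.

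Name one as primary. An unmatched t test on team rates is not a good substitute, because it becomes conservative when matching works. Apply the same principle to the secondary injury endpoints. Use the team-level or permutation version where counts are too sparse for a random-effect model: the assumptions above give only about 60 × 0.264 ≈ 16 lower-extremity injuries per arm, and knee or muscle injuries alone will be fewer.

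The cost is revised wording, a few lines of R and a somewhat wider interval. No new data are needed, since injuries and exposure are already collected by team and player. The synopsis dates this protocol version 28.09.2022 and the last participant out 30.06.2022. A change made after data collection should be documented and justified as a deviation, as section 5.1 requires.
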